10.4 End of Treatment

End of active study treatment is defined as 180 days post-therapy (+/- 30 days) at the time of the 6-month survey. Toxicity will also be assessed at this visit and appropriate follow up arranged.

10.5 Follow-up Period

Patients' electronic records at clinic visits q 6 months through year 3, then annually years 4 and 5, will be reviewed for recurrence and survival via for 5 years from randomization or until death. We expect that approximately 20% of patients may survive greater than 3 years.

10.6 End of Study

Patients lost to follow up will be documented and censored at time of last follow up for statistical consideration purposes. For protocol purposes, lost to follow up is defined as no contact with the subject for 12 months despite 3 documented attempts to follow up by the study team.

10.7 Early Withdrawal of Subject(s)

10.7.1 Criteria for Early Withdrawal

Subjects may voluntarily withdraw from the study at any time. The PI may also withdraw a subject from the study at any time based on his/her discretion. Reasons for PI-initiated withdrawal may include, but is not limited to the following:

- Adverse events
- Abnormal laboratory values
- Abnormal test procedure results
- Protocol deviation
- Administrative issues
- Disease progression
- Pregnancy

10.7.2 Follow-up Requirements for Early Withdrawal

Subjects who withdraw prior to study completion will be followed for primary and secondary end points via an intention to treat analysis. All attempts will be made to complete QOL surveys as appropriate.

Subjects may decline to complete surveys at any time during study participation; declining to complete surveys will be recorded and will not be considered a reportable protocol deviation.

10.7.3 Replacement of Early Withdrawal(s)

Subjects who withdraw prior to beginning protocol therapy may be replaced.

11 Study Assessments

11.1 Medical History

Prior to enrollment, all patients will have a complete medical History and Physical. Medical history will be documented in standard format including a history and physical exam by Gastroenterology, Medical Oncology or Radiation Oncology. Weekly treatment checks during radiation therapy will be focused histories.

11.2 Surveys

Written, verbal or electronic QOL surveys via the Functional Assessment of Cancer Therapy-Hepatobiliary (FACT-Hep, Version 4) and European Organization for Research and Treatment of Cancer Quality of Life Questionnaire Core-30 (QLQ-C30) will be performed at baseline and at 1, 3, and 6 months after the completion of PLA or HIGRT treatment.

12. SAFETY MONITORING AND REPORTING

The PI or treating MD is responsible for the identification and documentation of adverse events and serious adverse events, as defined below. At each study visit, the PI or designee must assess, through non-suggestive inquiries of the subject or evaluation of study assessments, whether an AE or SAE has occurred.

12.1 Adverse Events

An adverse event (AE) is any untoward medical occurrence in a subject receiving study therapy and which does not necessarily have a causal relationship with this treatment. For this protocol, the definition of AE also includes worsening of any pre-existing liver disease. An AE can therefore be any unfavorable and unintended or worsening sign (including an abnormal laboratory finding), symptom, or disease temporally associated with receiving either PLA or HIGRT. Abnormal laboratory findings without clinical significance (based on the PI's

judgment) should not be recorded as AEs. But laboratory value changes that require therapy or adjustment in prior therapy are considered adverse events.

From the time the subject signs the informed consent form through the End of Study visit (as defined in Section 11.4), all AEs must be recorded in the subject medical record and adverse events case report form.

AEs will be assessed according to the CTCAE version 4.0. If CTCAE grading does not exist for an AE, the severity of the AE will be graded as mild (1), moderate (2), severe (3), life-threatening (4), or fatal (5).

Attribution of AEs will be indicated as follows:

- Definite: The AE is clearly related to the study therapy
- Probably: The AE is likely related to the study therapy
- Possible: The AE may be related to the study therapy
- Unlikely: The AE is doubtfully related to the study therapy
- Unrelated: The AE is clearly NOT related to the study therapy

12.2 Serious Adverse Events

An AE is considered “serious” if in the opinion of the investigator it is one of the following outcomes:

- Fatal
- Life-threatening
- Constitutes a congenital anomaly or birth defect
- A medically significant condition (defined as an event that compromises subject safety or may require medical or surgical intervention to prevent one of the three outcomes above).
- Requires inpatient hospitalization or prolongation of existing hospitalization
- Results in persistent or significant incapacity or substantial disruption to conduct normal life functions.

12.2.1 Reporting of SAEs

SAEs will be reported to the IRB as per institutional policy.

12.3 Other Reportable Information

The study team will adhere to the institutional policy on subjects and pregnancy stringently.

13. QUALITY CONTROL AND QUALITY ASSURANCE

13.1 Data Management and Processing

13.3.1 Study Documentation

Study documentation includes but is not limited to source documents, case report forms, monitoring logs, appointment schedules, study team correspondence with regulatory bodies/committees, and regulatory documents that can be found in the “Regulatory Binder”, which includes but is not limited to signed protocol and amendments, approved and signed informed consent forms, FDA Form 1572, CAP and CLIA laboratory certifications, and clinical supplies receipts and distribution records.

13.3.2 Case Report Forms (CRFs)

A REDCap database will be the primary data storage method. Two parallel databases will be created to manage data for the VAMC and Duke trials. The CRFs will be updated in a timely manner following acquisition of new source data. Only the PI and select persons listed as key personnel on each trial are permitted to make entries, changes, or corrections in the CRF.

An audit trail will be maintained automatically by the electronic CRF management system, REDCap. All users of this system will complete user training, as required or appropriate per regulations.

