There are unique challenges within the VA patient population specifically with regards to the effective and efficient treatment of HCC. The VA has a higher portion of HCC patients than the average US population given higher base rates of HCV infection and alcoholic cirrhotic liver disease. Transplant options are limited due to extensive co-morbidities. Lack of easy access to a transplant center also creates geographic access issues. New limits on the Model for End Stage Liver Disease (MELD HCC) exception scores (now capped at 34 as of October 8, 2015) are already reducing overall transplant candidacy for many HCC patients. Alternative treatments to transplant and surgery based on strong evidence-based medicine are essential. This is particularly true in a new era of curative HCV treatment which -when combined with non-transplant based therapies for HCC- would potentially obviate the need for any additional therapies and break the cycle of cirrhosis, cancer and mortality.

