2.2.3 Data Analysis and Statistical Considerations

Ninety patients will be randomized with equal allocation to the two arms. Randomization will be stratified by whether the baseline global QOL score is < 60 or ≥ 60 , where QOL is measured by the EORTC QLQ-C30 scale (i.e., the European Organization for Research and Treatment of Cancer Quality of Life Questionnaire Core-30) which has a score range of 0-100. The primary outcome is the change in QOL from baseline to 1 month. We anticipate that approximately 10% of the accrued patients will be withdrawn before 1 month, leaving 80 evaluable patients to be used in the statistical analyses. The general linear model will be used to test for an arm effect (in patients receiving PLA vs HIGRT) by regressing the change in QOL on arm, controlling for the baseline value of QOL and the Child Pugh score. To calculate the power of the arm effect (in patients receiving PLA vs HIGRT) on change in QOL, we first note that the standard deviation of a normally distributed change score (SD_c) depends upon the SD of the pre-score, the SD of the post-score, and the Pearson correlation (ρ) between the two scores. If the SD's of the pre-score and the post-score are assumed equal and the correlation between them is 0.50, then $SD_c = SD$. For purposes of the power calculation, we assume that $SD=10$ and $\rho = 0.5$; therefore $SD_c = 10$. Assuming 40 evaluable patients per arm, the two-sample t-test (1-sided alpha = 0.10) of an arm difference in change across time in QOL has power 0.82 when the true arm difference in change score is 5 (i.e., 50% of SD_c). An arm difference of 50% of a standard deviation of an outcome variable is generally considered to be a "medium"-sized effect. In order to have 80 evaluable patients, 90 patients will be accrued (assuming ~10% drop out prior to the 1 month EOTRC QOL-C30 questionnaire).

After randomization, patients who have consented to study, but in the clinical judgement of the treating physician are no longer candidates for the randomized treatment, will continue to be evaluable for all study endpoints if treated with MWA or HIGRT (per PI approval). The primary analysis will be intent-to-treat (i.e., treatment arm as randomized). A sensitivity analysis will be conducted with patients categorized by treatment received.

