Ninety patients will be randomized with equal allocation to the two arms. Randomization will be stratified by whether the baseline global QOL score is < 60 or ≥ 60 , where QOL is measured by the EORTC QLQ-C30 scale. We anticipate that approximately 10% of the accrued patients will withdraw before 1 month, leaving 80 evaluable patients to be used in the statistical analyses. The general linear model will be used to test for an arm effect (in patients receiving PLA vs HIGRT) by regressing change across time in QOL on arm, controlling for the baseline value of QOL, Child Pugh score, and time between baseline and end of treatment. To calculate the power of the arm effect (in patients receiving PLA vs HIGRT) on change in QOL, we first note that the standard deviation of a normally distributed change score (SD_C) depends upon the SD of the pre-score, the SD of the post-score, and the Pearson correlation (ρ) between the two scores. If the SD's of the pre-score and the post-score are assumed equal and the correlation between them is 0.50, then $SD_C = SD$. For purposes of the power calculation we assume that $SD=10$ and $\rho = 0.5$; therefore $SD_C = 10$. Assuming 40 evaluable patients per arm, the two-sample t-test (1-sided alpha = 0.10) of an arm difference in change across time in QOL has power 0.82 when the true arm difference in change score is 5 (i.e., 50% of SD_C). An arm difference of 50% of a standard deviation of an outcome variable is generally considered to be a "medium"-sized effect. In order to have 40 evaluable patients per treatment arm, 90 patients will be accrued (assuming drop out prior to the 1 month EORTC QOL-C30 questionnaire).

After randomization, patients may decline the randomized treatment but will continue to be evaluable for all study outcomes if treated with MWA or HIGRT. All endpoints will be analyzed per randomized arm and per treatment delivered. If the patient does not receive either SBRT or MWA, the patient will be withdrawn from the study.

Secondary Endpoints:

[figure not shown]

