1. *To estimate the change in QOL in patients receiving PLA vs HIGRT, as measured by EORTC C-30, from baseline to 3 months post-treatment.* The mean difference between arms in change from baseline to 3 months in QLC-C30 will be estimated with their 95% confidence intervals [CI]. To calculate these CI's, the mean arm difference in QOL and its standard error will be estimated from a general linear model in which change in QOL is regressed on arm, controlling for the baseline value of QOL and the Child Pugh score.
2. *To estimate the change in QOL in patients receiving PLA vs HIGRT, as measured by EORTC C-30, from baseline to 6 months post-treatment.* The mean difference between arms in change from baseline to 6 months in QLC-C30 will be estimated with their 95% confidence intervals [CI]. To calculate these CI's, the mean arm difference in QOL and its standard error will be estimated from a general linear model in which change in QOL is regressed on arm, controlling for the baseline value of QOL and the Child Pugh score.

3. *To estimate the change in QOL as measured by FACT-Hep in patients receiving PLA vs HIGRT.* Change in FACT-Hep score from baseline to 1 month, baseline to 3 months and baseline to 6 months will be calculated for each patient, and the mean arm difference in change will be estimated with its 95% CI. The CI will be estimated as described for Secondary Objective 1.
4. *To estimate grade ≥ 2 acute toxicity within 90 days of treatment initiation.* CTCAE version 4 will be used for all toxicity assessments. The acute toxicity rate will be defined as any grade 2+ toxicity occurring during treatment through 90 days post-PLA or post-HIGRT. The acute toxicity rate with its exact 95% confidence interval will be estimated within each arm. The arm difference in acute toxicity rate will be estimated with its 95% CI. We will also estimate the rate of hospitalization due to treatment complications with its 95% CI and the proportion of patients requiring treatment breaks longer than 7 days from HIGRT, with its 95% CI.

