7.1.2 Randomization

Patients will be sequentially randomized with equal allocation to the two arms in Research Electronic Data Capture (REDCap).

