Before conducting any study-specific procedures, the Principal Investigator or designee must obtain informed consent from the subject. The original informed consent form will be stored with the subject's study records and a copy of the informed consent form will be provided to the subject. This discussion will occur in a location that ensures subject privacy and in a manner that minimizes the possibility of coercion. The Principal Investigator is responsible for asking the subject whether the subject wishes to notify his/her primary care physician about participation in the study. If the subject agrees to such notification, the Principal Investigator will inform the subject's primary care physician about the subject's participation in the clinical study.

16 Study Documentation

See section 13.3.1 for details regarding documentation and case report forms.

17 Privacy, Confidentiality, and Data Storage

The Principal Investigator will ensure that subject privacy and confidentiality of the subject's data will be maintained. Research Data Security Plans (RDSPs) will be approved by the appropriate Institutional Site Based Research group (Duke IRB and the Durham VAMC IRB).

To protect privacy, every reasonable effort will be made to prevent undue access to subjects during the course of the study. All research related interactions with the participant will be conducted by qualified research staff who are directly involved in the conduct of the research study.

To protect confidentiality at Duke, subject files in paper format will be stored in secure cabinets under lock and key accessible only by the research staff. Electronic records of subject data will be maintained using a dedicated database (REDCap), which is housed in an encrypted and password-protected DCI file server. Access to electronic databases will be limited to specified key personnel. Key personnel who enter study data for subjects participating at Duke will not have any visibility on the data entered for subjects participating at the Durham VAMC. The security and viability of the IT infrastructure will be managed by the DCI and/or Duke Medicine.

Upon completion of the study, research records will be archived and handled per DUHS HRPP policy.

Subject names or identifiers will not be used in reports, presentations at scientific meetings, or publications in scientific journals.

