- De-Identified (all HIPAA 18 and study ID/code removed):
 - Verified Statistically
 - OR
 - Verified by Absence or Removal of HIPAA 18 and study ID
- Limited Data Set
- Other: Describe: _____

4. Location of Data and/or Specimens, and Data Retention Plan:

- A. Data and/or Specimen Location: To protect confidentiality, subject files in paper format will be stored in a secure, locked office. Subjects will be identified only by a unique study number. Electronic records of subject data will be maintained using a dedicated database, which is housed in an encrypted and password-protected file server. For the patients enrolled at the VA, access to electronic databases will be limited to the research study team in the VA departments of Radiation Oncology and Medicine (Gastrointestinal). The security and viability of the IT infrastructure will be managed by the Durham VA for VA patients. Data will be stored electronically in a VA instance of REDCap and on <S:\RADIATIONONCOLOGY\Research\HCC Study>. All data will be stored electronically.
- Data will be also be placed at the VA Informatics and Computing Interface (VINCI); <http://vaww.vinci.med.va.gov/vincicentral/VINCIWorkspace.aspx>. The VA Informatics and Computing Infrastructure is a partnership between the VA Office of Information Technology and the Veterans' Health Administration Office of Research and Development. Researchers and operations staff can use VINCI to access data and statistical analysis tools in a virtual working environment through a certified VHA network computer using the VA Intranet or Virtual Private Network (VPN).

B. Data Retention Plan

Research records will be maintained and destroyed according to the National Archives and Records Administration, Records Schedule Number: DAA-0015-2015-0004. Records destruction, when authorized, will be accomplished using the then current requirements for the secure disposal of paper and electronic records. Currently, destruction of research records (see DAA-0015-2015-0004, section 7.6 "Research Investigator Files" for materials included in research records) is scheduled for 6 years after the cut-off (the cut-off is the completion of the research project) and may be retained longer if required by other federal agencies. Records will not be destroyed without pre-notification to the facility records manager. .

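### Site (Durham VA or Duke) is in none of the QOL models, and the plan does not say whether allocation runs on one list or one per site; adding site is a minor, nearly free improvement

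*Combined protocol and SAP*

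**What the plan says.** The primary analysis is described twice. Section 2.2.3 tests the arm effect "by regressing the change in QOL on arm, controlling for the baseline value of QOL and the Child Pugh score". Section 4 describes the same test "controlling for the baseline value of QOL, Child Pugh score, and time between baseline and end of treatment". For the secondary EORTC comparisons at 3 and 6 months, Section 4 says "change in QOL is regressed on arm, controlling for the baseline value of QOL and the Child Pugh score", and the FACT-Hep intervals follow the same method. Site appears in none of these.

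On allocation, Section 7.1.1 forms two strata, baseline QLQ-C30 below 60 and 60 or above. Section 7.1.2 adds: "Patients will be sequentially randomized with equal allocation to the two arms in Research Electronic Data Capture (REDCap"). Neither section mentions site or the number of allocation lists.

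On data systems, Section 13.3.2 says "Two parallel databases will be created to manage data for the VAMC and Duke trials". Section 17, item 4, says of VA patients: "Data will be stored electronically in a VA instance of REDCap". Section 17 also says that staff entering Duke data "will not have any visibility on the data entered for subjects participating at the Durham VAMC". The Section 5 heading says that patients from the two institutions are pooled.

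**The concern.** Randomisation takes place in REDCap, and the two institutions hold their data in separate REDCap databases with restricted visibility between them. The protocol does not explain how one allocation sequence would work across them, so separate sequences per site are plausible. In that case site is a factor in the design, the real number of strata is four (site by QOL) rather than two, and the models leave out a factor on which the arms were balanced. The reported standard error would then include between-site variation that the design had already removed from the comparison.

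If there is one list, site is simply a baseline factor, known for every patient, that can fall unevenly between arms by chance. Leaving it out does not invalidate the analysis, but it gives up precision if the sites differ in mean QOL change. At stake is some power and interval width in a trial planned at 0.82 power, not the validity of a positive result.

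**Working it through.** **Inputs from the documents (Sections 2.2.3 and 4).** 40 evaluable patients per arm, true difference 5, SD of change 10, one-sided alpha 0.10, stated power 0.82.

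**Inputs assumed, because the documents give none.** Site share w = 0.5 (0.3 as a check); difference D between sites in mean QOL change of 2, 5 or 10 points; SD 10 within site.

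**Step 1: the plan's own figure.** SE = 10 × √(2/40) = 2.236. Power = Φ(5/2.236 − 1.2816) = Φ(0.954) = 0.830. The noncentral t with 78 degrees of freedom gives 0.827. The stated 0.82 is reproduced to within rounding.

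**Step 2: inflation factor.** With site omitted, the residual variance rises from 100 to 100 + w(1−w)D². The reported SE is multiplied by k = √(1 + w(1−w)D²/100). For w = 0.5: D = 5 gives √1.0625 = 1.031; D = 10 gives √1.25 = 1.118.

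**Step 3: lists balanced within site, site omitted.** The true SE of the arm difference stays at 2.236, but the reported SE is 2.236k. Real one-sided size = 1 − Φ(1.2816k). Power = Φ(2.236 − 1.2816k). Coverage of a nominal 95% interval = 2Φ(1.96k) − 1.

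| D | w | k | Real size | Power, no site | 95% CI coverage |
|---|---|---|---|---|---|
| 2 | 0.5 | 1.005 | 0.099 | 0.828 | 0.951 |
| 5 | 0.5 | 1.031 | 0.093 | 0.820 | 0.957 |
| 5 | 0.3 | 1.026 | 0.094 | 0.822 | 0.956 |
| 10 | 0.5 | 1.118 | 0.076 | 0.789 | 0.972 |
| 10 | 0.3 | 1.100 | 0.079 | 0.796 | 0.969 |

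With site in the model, size returns to 0.10 and power to 0.83.

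**Step 4: one list, not stratified by site, site omitted.** The true SE is also 2.236k, so the reported SE is correct and the size is 0.10. Power = Φ(5/(2.236k) − 1.2816). For w = 0.5: D = 5 gives Φ(2.169 − 1.2816) = 0.81; D = 10 gives Φ(2.000 − 1.2816) = 0.76. For w = 0.3 the values are 0.82 and 0.77. With site in the model, power is about 0.83. The chance shift of the estimate from site imbalance has SD of about D × √(w(1−w)) × √(2/40). For w = 0.5 that is 0.56 points at D = 5 and 1.12 at D = 10.

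**Step 5: simulation.** N = 80, 8,000 runs per setting. Within-site lists without a site term gave size 0.096 to 0.097 at D = 5 and 0.077 to 0.079 at D = 10, with power 0.819 to 0.821 and 0.780 to 0.792. One list without site gave size 0.095 to 0.102, with power 0.811 to 0.819 at D = 5 and 0.766 to 0.771 at D = 10. Adding site gave power of 0.824 to 0.831 in all these settings with D = 5 or 10.

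**Step 6: a different variance assumption.** Adjusting for baseline with correlation 0.5 leaves a residual SD of 10 × √(1 − 0.25) = 8.66, variance 75. If the site effect is part of that 75, its share is w(1−w)D²/75: 8% at D = 5 and 33% at D = 10 for w = 0.5. The real size for within-site lists, 1 − Φ(1.2816/√(1 − share)), is then 0.090 and 0.058. The direction is the same and the effect somewhat larger.

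**The case against.** The strongest objection is that separate lists are nowhere stated. A reader might infer from the parallel databases that randomisation runs in two separate systems, and that the planned standard errors therefore do not match the allocation. The documents do not support that as a finding. Section 13.3.2 describes the databases as a means of managing data, and the Section 17 text concerns storage and access. Section 7.1.1 names two QOL strata, whereas per-site lists would make four. With one list the standard error without site is valid. This objection stands: the mismatch is conditional.

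A reader might also take the Background statement, "There are unique challenges within the VA patient population", as evidence that VA patients differ in prognosis from Duke patients. The comparison there is with the average US population, not with Duke. Both sites enrol non-surgical patients (or those declining surgery) under the same Child-Pugh and ECOG limits, and the model already adjusts for baseline QOL and Child-Pugh score. A remaining site effect on QOL change is possible but not documented.

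Third, the harm is small. A 5-point site difference equals the whole target effect, yet under within-site lists it lowers power only from 0.83 to 0.82. At 2 points the loss is negligible. Chance site imbalance under one list is not bias, because the standard error covers it. All of this is right and limits the point to a minor one. It does not remove the case for a covariate that is already known and costs one degree of freedom.

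**Conclusion.** The point holds as a minor, nearly free improvement. That site is missing from every QOL model is certain from the text. That allocation runs separately by site is plausible, with moderate confidence, and should be clarified rather than asserted.

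Under within-site lists, equal site shares and an SD of 10, site differences of 5 to 10 points bring the real one-sided size to about 0.093 to 0.076 and power to about 0.82 to 0.79, against 0.83 with site. Under one list, size is correct and power is about 0.81 to 0.76, against 0.83. The site shares and differences are illustrations. The consequence is conservative or a loss of precision in every case examined; nothing here inflates the false-positive rate or threatens a positive result.

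**What to change.** 1. Add site (VA or Duke) as a fixed covariate in the primary QOL model, in both Section 2.2.3 and Section 4, and in the secondary EORTC and FACT-Hep models. In the same edit, reconcile the two covariate lists for the primary model, since time between baseline and end of treatment appears only in Section 4.
2. State in Sections 7.1.1 and 7.1.2 whether allocation uses one list or one per site. Name site as a stratification factor only if lists are per site; if there is one list, that statement would be untrue, and no change to the randomisation is asked for.

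The cost is a few lines of text and one degree of freedom. Site is already known from the database that holds each patient. The covariate should be named before outcomes are analysed by arm, so that it is not open to challenge as post hoc.
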